10.3.2 Stopping Rules for valve-in-MAC stratum

The study will be monitored to ensure that the mortality with 30-days after the procedure does not substantially exceed an anticipated rate. We anticipate the rate of 30-day mortality is 30% or less and determine the stopping rule by a Bayesian approach 25 . The stopping boundary is reached if the posterior probability that the 30-day mortality rate exceeds 30% is at least 90%. We take our prior distribution to be a beta distribution so that our prior clinical opinion is worth 20% of the weight we will place on the new data. This gives the prior parameters a = 1.8, b = 4.2. Hence when we make decisions about stopping the study, the data from the study will dominate over the prior opinion.

The following table summarizes the threshold numbers for the stop rule boundary, which would lead to a recommendation to stop the study due to the excess 30-day mortality.

Number of subjects in the "valve-in- MAC" stratum	Stop if the number of deaths within 30 days reaches
3	3
4-6	4
7-8	5
9-11	6
12-14	7
15-16	8
17-19	9
20-22	10
23-25	11
26-27	12
28-30	13

We investigated the performance of the above stopping rule by a simulation study. In each simulation run, we generated a study with 30 independent Bernoulli trials, each with a true certain 30-day mortality, and compared these outcomes with the above stopping boundary to determine whether the study was stopped. We repeated the simulation 100,000 times and computed the proportion of stopped studies using the above stopping rule. The following table summarizes the performance of this stopping rule:

True 30-day mortality rate	20%	25%	30%	35%	40%	45%	50%	55%
Proportion of Stopped Studies (%)	3.9	10.2	21.8	38.9	58.5	76.6	89.1	95.9
Average number of subjects	29.2	28.1	26.1	23.3	20	16.4	13.2	10.5
Average number of 30-day mortality	5.8	7	7.8	8.2	8	7.4	6.6	5.8

These simulation results suggest that our stopping rule has a low probability stopping a study when the true 30-day mortality rate is 30% or less, and the probability of stopping a study is high when the true 30-day mortality rate exceeds 30%. There, we believe that our Bayesian stopping rule for 30-day mortality has satisfactory statistical properties.

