10.3 Stopping Rules and Data Safety Monitoring

A Data Safety and Monitoring Board (DSMB) appointed by the NHLBI Division of Intramural Research will monitor the safety of subjects in the study as described in the investigational plan. All members of the DSMB are unaffiliated to the study. The NHLBI DSMB will review the protocol progress report at sixmonth intervals. The DSMB may recommend early termination of the study for considerations of safety and efficacy. Unanticipated Adverse Device Effects (UADEs) will be submitted to the DSMB following the same timelines as the IRB (See section 9.2.4).

In the case of death or serious UADE, if the sponsor and the principal investigator determine that the event presents an unreasonable risk to the participating subjects, the clinical trial will be terminated within 5 working days after making that determination and not later than 15 working days after the sponsor first receives notice of the effect. [21 CFR 812.46]. All clinical sites will be notified of this action.

Each institutional IRB will review all Serious Adverse Events, Unanticipated Adverse Device Effects, and Unanticipated Problems, and may choose to suspend or terminate the protocol based on those findings. We believe this will protect subject safety.

Stopping rules were changed in Amendment A to be more statistically robust, to accommodate two strata of patients, and to focus on 30-day survival. There are two clearly different strata of subjects to be enrolled in this study. For TMVR in the setting of prior annuloplasty (aka "valve-in-ring" or "valve-in-band"), the risk of valve migration and of severe paravalvular leak, attendant mortality, are much lower. For TMVR in the setting of mitral annular calcification (aka "valve-in-MAC"), patients are older and have more comorbidity, and the procedures are much more technically complex. Accordingly, valve-in-MAC TMVR has higher mortality. The reported 30-day mortality of valve-in-MAC in the global registry of 64 patients was $30\%^{14}$.

We propose two different stopping rules, one for valve-in-ring and valve-in-band, and another for valve-in-MAC. While rules are provided for up to 30 subjects in each stratum, the total treated within both strata combined will not exceed 30.

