10.3.1 Stopping Rules for valve-in-ring and for valve-in-band stratum

The study will be monitored to ensure that the mortality with 30-days after the procedure does not substantially exceed an anticipated rate. We anticipate the rate of 30-day mortality is 10% or less and determine the stopping rule by a Bayesian approach 25 . The stopping boundary is reached if the posterior probability that the 30-day mortality rate exceeds 10% is at least 90%. We take our prior distribution to be a beta distribution so that our prior clinical opinion is worth 20% of the weight we will place on the new study data, which gives the prior parameters a = 0.6, b = 5.4. Hence when we make decisions about stopping the study, the data from the study will dominate over the prior opinion.

The following table summarizes the threshold numbers for the stop rule boundary, which would lead to a recommendation to stop the study due to the excess 30-day mortality.

Number of subjects in the stratum	Stop if the number of deaths within 30 days reaches
2-4	2
5-10	3
11-17	4
18-24	5
25-30	6

We investigated the performance of the above stopping rule by a simulation study. In each simulation run, we generated a study with 30 independent Bernoulli trials, each with a true certain 30-day mortality, and compared these outcomes with the above stopping boundary to determine whether the study was stopped. We repeated the simulation 100,000 times and computed the proportion of stopped studies using the above stopping rule. The following table summarizes the performance of this stopping rule:

True 30-day mortality rate	5%	10%	15%	20%	25%	30%	35%	40%
Proportion of Stopped Studies	2.9%	16.9%	42.1%	68.7%	86.0%	94.9%	98.6%	99.7%
Average number of subjects	29.4	27	22.8	17.9	13.8	10.6	8.2	6.6
Average number of 30-day mortality	1.5	2.7	3.4	3.6	3.4	3.2	2.9	2.7

These simulation results suggest that our stopping rule has a low probability stopping a study when the true 30-day mortality rate is 10% or less, and the probability of stopping a study is high when the true 30-day mortality rate exceeds 10%. There, we believe that our Bayesian stopping rule for 30-day mortality has satisfactory statistical properties.

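### The stopping-rule performance tables assume 30 subjects in one stratum, but the two strata share a cap of 30, so with mixed enrolment the printed probabilities fit neither possible scope of a crossing

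*Combined protocol and SAP*

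**What the plan says.** Section 10.3 sets up separate rules because the strata differ in risk: "We propose two different stopping rules, one for valve-in-ring and valve-in-band, and another for valve-in-MAC". It adds that boundaries are listed up to 30 subjects for either stratum, but "the total treated within both strata combined will not exceed 30".

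- **Ring/band (10.3.1).** "We anticipate the rate of 30-day mortality is 10% or less". The boundary is a posterior probability of at least 90% that mortality exceeds 10%, with a Beta(0.6, 5.4) prior.
- **MAC (10.3.2).** "We anticipate the rate of 30-day mortality is 30% or less". The boundary is the same 90% threshold against 30%, with a Beta(1.8, 4.2) prior.

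Both sections give the same consequence of reaching the boundary, "which would lead to a recommendation to stop the study due to the excess 30-day mortality". Both evaluate the rule by simulating 30 Bernoulli outcomes at one mortality rate. The printed stop proportions at the anticipated rates are 16.9% (ring/band at 10%) and 21.8% (MAC at 30%). Section 10.3.1 concludes that "our stopping rule has a low probability stopping a study when the true 30-day mortality rate is 10% or less" and that it is high above that rate. Section 10.3.2 says the same about 30%.

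No section gives an expected split between strata, results for a stratum smaller than 30, or the chance that either boundary is crossed.

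**The concern.** Each table holds only if all 30 subjects fall in that one stratum. Any mixed enrolment makes both strata smaller than the tables assume, so neither table describes the rule that the DSMB would apply.

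Which figures are needed depends on what a crossing does, and this is unclear. The consequence is worded as stopping the study, while the headings, the boundary tables and the rationale in 10.3 are all by stratum.

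- If a crossing acts on the stratum, the DSMB needs the performance of each rule at a realistic stratum size. A smaller stratum gives the rule fewer chances to cross, for good and for bad reasons.
- If a crossing acts on the whole study, the DSMB needs the chance that either boundary is crossed with 30 subjects in total. Deaths in one stratum would then also close the other, which the two-stratum rationale does not discuss.

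At stake is whether the low and high stopping probabilities claimed for a mortality safeguard hold in the trial as it can actually enrol.

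**Working it through.** **Inputs.** Boundaries, priors, thresholds and printed proportions are from 10.3.1 and 10.3.2. The cap of 30 is from 10.3. The split between strata is an assumption, and a range is shown. Outcomes are checked after every subject with 30-day status known.

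**Step 1: boundaries.** For each n from 1 to 30, find the smallest d with P(rate > p0 | Beta(a + d, b + n − d)) ≥ 0.90. Both printed tables agree at every n.

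**Step 2: printed performance.** Let S(n, d) be the probability of d deaths among n subjects with no crossing so far, and p the true mortality. Then S(n, d) = (1 − p)·S(n − 1, d) + p·S(n − 1, d − 1), and any mass with d at or above the boundary is moved to stopped. For example, the first possible MAC crossing is 3 deaths in 3, with probability 0.3³ = 2.7%. With 30 subjects in the stratum the exact stop probabilities are 17.1% for ring/band at 10% (printed 16.9%) and 21.8% for MAC at 30% (printed 21.8%). All 16 printed proportions reproduce within 1 point. The tables are correct for what they simulate.

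**Step 3: crossing acts on the stratum.** The same recursion at smaller stratum sizes gives:

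| Stratum, true mortality | Printed (n = 30) | n = 20 | n = 15 | n = 10 |
|---|---|---|---|---|
| Ring/band, 10% | 16.9% | 13.6% | 11.3% | 9.6% |
| Ring/band, 20% | 68.7% | 53.7% | 44.7% | 36.2% |
| MAC, 30% | 21.8% | 17.6% | 15.2% | 10.5% |
| MAC, 50% | 89.1% | 76.1% | 66.9% | 48.5% |

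The rows at 10% and 30% are false stops at the anticipated rates; the other two are detection of excess mortality. At 15 per stratum, detection is lower than printed by 68.7 − 44.7 = 24.0 points and 89.1 − 66.9 = 22.2 points.

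**Step 4: crossing acts on the study.** With independent strata, P(either crossed) = 1 − (1 − P_ring)(1 − P_MAC), total 30, true rates exactly 10% and 30%:

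- 10 ring/band, 20 MAC: 1 − (1 − 0.0960)(1 − 0.1755) = 25.5%
- 15 and 15: 1 − (1 − 0.1132)(1 − 0.1519) = 24.8%
- 20 and 10: 1 − (1 − 0.1356)(1 − 0.1048) = 22.6%

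For splits with 4 to 19 ring/band subjects it is 24.0% to 25.5%. Over all splits it runs from 16.3% (28 and 2) to 25.5% (16 and 14). The excess over the highest printed figure at the anticipated rates is at most 25.5 − 21.8 = 3.7 points. At true rates of 5% and 20% the figure is 2.8% to 5.6% over all splits, and 5.5% at 15 and 15.

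**The case against.** The best defence has four parts.

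- **Scope.** The sections also use the word study for a single simulated one-stratum run, the headings and boundary tables refer to the stratum, and 10.3 sets two rules because the strata differ. A per-stratum reading is plausible. This stands. A reader might infer that the protocol plainly orders whole-study closure and so hides a false-stop rate of one in four. The wording is too ambiguous for that, and the figure needs mixed splits and true rates exactly at the anticipated values, which are stated as upper limits.
- **Disclosure.** Section 10.3 says openly that the combined total will not exceed 30, and the tables are right for a stratum of 30. Both are true, but the performance figures and the conclusions drawn from them were not adjusted to that cap.
- **Size.** The either-boundary figure barely exceeds the printed 21.8%, and at 25 and 5 it is 19.5%, below it. This stands. Combining the two printed figures, 1 − 0.831 × 0.782 = 35.0%, would be wrong because it assumes 60 subjects.
- **Consequence.** A crossing leads to a recommendation, an independent DSMB oversees the study, and the analysis is descriptive. This limits the harm and means that no efficacy error rate is affected. It does not supply the missing figures.

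A reader might also contrast a 40.2% chance of stopping the study (15 and 15, true rates 5% and 40%) with 2.3% from the ring/band rule alone. That is not false stopping: the MAC rule alone accounts for 38.8%, by detecting mortality truly above its 30% limit. The contrast shows only why the scope must be stated.

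**Conclusion.** The point holds under either reading of the rule. With mixed enrolment, the printed stopping probabilities belong to a design that the trial cannot have.

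- **Stratum scope:** the tables overstate both false stopping and detection. The loss of detection matters more: at 15 per stratum it is over 20 points in both examples, and 44.7% at twice the anticipated ring/band mortality is hard to call high.
- **Study scope:** the relevant probability is missing, but it is no more than about 4 points above the highest figure printed at the anticipated rates, and lower if true mortality is below the anticipated rates. The documents do not support a claim of large hidden inflation.

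The boundaries are correctly derived and are not in question. The results assume independent strata, a fixed split, continuous checking with complete 30-day outcomes (as the protocol's own simulation does), and a total of 30. Section 10.1 allows the sample size to be increased, in which case the either-boundary figure could be higher. The change should be made, but it is a restatement of operating characteristics and not a redesign.

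**What to change.** 1. Reconcile 10.3.1 and 10.3.2 with the two-stratum rationale in 10.3 by stating whether a crossing acts on the stratum or on the whole study. This review does not say which it should be.
2. Replace the two performance tables with results at a total of 30 over a stated range of plausible splits: stop probabilities per stratum and, if whole-study scope is kept, the probability that either boundary is crossed.
3. Rewrite the closing statements about low and high stopping probability to match those results.

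The cost is one sentence and a rerun of the existing simulation; the boundary tables can stay as they are. The downside is that the detection figures (stratum scope) or the false-stop figure (study scope) will look less favourable than those printed now.

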10.4 Off study criteria

- Completion of the 5-year follow-up
- The subject voluntarily withdraws
- Significant subject non-compliance with follow-up visits
- Death

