6.4 Time and Events Schedule

	Screening	Baseline	Day 0	Inpatient	30 d (±14d) FU	6 mo (± 30 Days)	12 mo (± 4 wk)	2 yrs (± 1 mo) (range)	3 yrs (± 1 mo)	4 yrs (± 1 mo)	5 yrs (± 1 mo)
Baseline informed consent:		Х									
Multidisciplinary heart team eligibility determination		х									
Baseline clinical assessment		Х									
6 minute walk test		Х			Х		Χ				
Kansas City Cardiomyopathy Questionnaire (KCCQ)		х			Х		Х				
NYHA Classification		Х			Х	Х	Χ				
Frailty tests: Katz ADL, 5MW, Albumin		Х									
Blood tests: CBC, Platelet, Haptoglobin, Liver panel, Chemistry Panel, Albumin, LDH, BNP/Pro-BNP (as clarified below)		Х		Х	Х	Х	Х				
Vital signs and in-person visit		Х			Χ	Χ	Χ				
Cardiac CT contrast-enhanced gated dy- namic	Screening or baseline	Screening or baseline		Inpatient or 30D	Inpatient or 30D						
Transesophageal echocardiogram	Screening or baseline	Screening or baseline	Х								
TMVR with LAMPOON			Χ								
Surface echocardiogram	Screening or baseline	Screening or baseline		Х	Х	Х	Х				
ECG		Х		Х	Χ	Х	Χ				
Adverse event assessment				Х	Χ	Χ	Χ				
Vital status and clinical echo or report								Χ	Χ	Χ	Χ

Subjects would receive continuing care from their primary physicians with consultant input as requested from the structural heart disease program.

For subjects who die, necropsy evaluation is requested to examine the heart at NIH.

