12 month (±30 days)	Clinic/office visit to update subject's vital status to include:
	 Vital signs ECG Medication Assessment NYHA Classification Surface Echocardiogram 6-minute walk
	 Kansas City Cardiomyopathy Questionnaire Blood work to include: CBC with platelets Haptoglobin Chemistry Panel PT INR BNP/Pro-BNP Adverse Event Assessment
Annually years 2-5 (\pm 30 days)	 Telephone call or local physician contact to assess vital status Collect results or images of clinical echocardiogram

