10.2.5 Independent Clinical Events Adjudication

An independent Clinical Events Adjudication Committee will review all of the following that occur in the first year:

- Deaths
- Primary endpoints
- Valve embolization events
- Site-reported strokes

The CEAC will classify relatedness of the above events to the LAMPOON procedure.

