11.2.3 Adverse Event Reporting

Adverse event recording will start on Day (0) of the LAMPOON TMVR procedure and will continue through the 12-month Follow Up. New events or conditions present at baseline that increase in severity will be recorded and evaluated and reported on the case report form. Once the subject has completed the 30-day follow up, only serious adverse events (SAE), serious adverse device effects (SADE), unanticipated device effects (UADE) and unanticipated problems (UP) will be reported to the Sponsor. It is the responsibility of the site investigator to report adverse events and adverse device effects to their respective IRBs or other regulatory bodies according to their reporting requirements. Monitoring visits will be conducted by the Sponsor to review source documentation, and accuracy and completion of the adverse event case report forms.

11.2.4 Adverse event reporting timeframes:

Serious Adverse Events (SAEs)

- All serious adverse events will be reported to the Sponsor immediately but not later than 3
 working days from the event. The respective institutional IRB should be notified according to
 their requirements.
- The serious adverse event will be evaluated by the sponsor. If determined to be an unanticipated adverse device effect that increases the risk to the participating subjects, the sponsor will terminate the investigation within 5 days after making the determination, and not later than 15 working days after the sponsor was first notified of the event. [21 CFR 812.46]

Unanticipated Adverse Device Effects (UADE)

- Must be reported to the Sponsor and the institutional IRB immediately but no later than 10 working days after the investigator learns of the event. [21 CFR 812.150]
- Unanticipated Adverse Device Effects should be reported via telephone as well as on the adverse event section of the case report form.
- If the event is determined by the Sponsor to be a UADE, the Sponsor will report the event to all investigators to enable reporting to their respective IRB/regulatory bodies. The Sponsor will provide this notification to participating sites and to the FDA within 10 working days after they first receive notice of the effect. [21 CFR 812.150]

 All Unanticipated Adverse Device Effects will be reported by the Sponsor to the NIH IRB per NIH Policy 801 "Reporting Research Events".

Deaths

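### Section 10.4 lets missed visits take a subject who has not withdrawn consent off study, and the protocol does not provide for collecting vital status or events afterwards

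*Combined protocol and SAP*

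**What the plan says.** Section 10.4 is a list of four off-study criteria: completing five years of follow-up, voluntary withdrawal, "Significant subject non-compliance with follow-up visits", and death. It does not say how many missed visits count as significant, what attempts at contact come first, or who decides. It also does not say what data, if any, are sought afterwards.

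Other sections set out what is due over the same period:

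- **First year, adjudication (10.2.5):** "An independent Clinical Events Adjudication Committee will review all of the following that occur in the first year". The list includes deaths and "Site-reported strokes".
- **First year, safety (11.2.3):** recording of adverse events "will continue through the 12-month Follow Up", restricted after the 30-day visit to serious and unanticipated events.
- **First year, contact (6.5):** clinic or office visits at 30 days, 6 months and 12 months.
- **Years 2 to 5 (6.5):** "Telephone call or local physician contact to assess vital status" and "Collect results or images of clinical echocardiogram". The matching row in the 6.4 table is "Vital status and clinical echo or report".

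On deaths, section 11.2.4 requires the investigator to tell the sponsor within 3 working days of being notified.

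**The concern.** Withdrawal of consent has its own line in 10.4, so the non-compliance line must cover people who have not withdrawn. Such a person may be unable or disinclined to travel but still reachable by telephone or through a physician. Taking that person off study because of missed visits risks losing information that does not depend on visits.

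The outcomes at stake are vital status after 30 days, deaths and strokes due for first-year adjudication, serious adverse events up to 12 months, and vital status and clinical echo reports in years 2 to 5. The loss would be avoidable. It could also be informative if attendance is related to health. The documents do not indicate which way any bias would run. Section 14.7 asks for missing data to be explained, but no section says how missing outcomes are to be analysed.

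The 6-minute walk, KCCQ, protocol echocardiogram and study blood tests need attendance. They are lost when a visit is missed whatever 10.4 says, and are not part of this point.

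**Working it through.** The plan gives no figure for non-compliance or dropout, so there is none to reproduce. The check is a comparison of the text, followed by simple arithmetic.

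**1. What going off study ends.** Section 10.4 gives the non-compliant subject the same status as one who has completed five years or has died. The ordinary reading is that scheduled study contact stops. No available section resumes it by telephone, records or physician contact. The annual contacts in 6.5 are scheduled activities and are not extended to subjects who have gone off study. The death clause in 11.2.4 runs from notification, so it does not require a site to ask.

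**2. Whether a visit is needed.** For vital status and clinical echo reports it is not, since 6.5 obtains both in years 2 to 5 by telephone, physician or existing reports. Deaths, strokes and serious adverse events in the first year could be asked about in the same way.

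**3. Effect of one unknown vital status.** With n treated, d known deaths and m unknown, the best case is d/n and the worst case is (d + m)/n. The width is m/n, whatever d is.

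| n | Source | Width for m = 1 |
|---|---|---|
| 30 | Section 10.1 | 1/30 = 3.3 points |
| 20 | Assumed stratum size | 1/20 = 5.0 points |
| 15 | Assumed stratum size | 1/15 = 6.7 points |
| 10 | Assumed stratum size | 1/10 = 10.0 points |

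Section 10.2 stratifies the analysis by valve setting but does not give the split, so the last three rows are illustrations. No mortality or dropout rate is assumed.

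**4. Contacts at stake.** Years 2, 3, 4 and 5 give at most 4 annual contacts for a subject removed before year 2.

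**5. Timing, on the protocol's own estimates.** The front matter estimates completion on December 31, 2023, and section 1.0 gives five years per participant.

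- Last procedure: December 31, 2023 minus 5 years = December 31, 2018.
- Close of the last 12-month window: plus 12 months plus 30 days = January 30, 2020. This is before the version date of 2020-08-24 in the Appendix A footer.
- Contacts still due at that version date: a procedure in April 2017 (expected start, 12.2.2) leaves years 4 and 5, which is 2. A procedure on December 31, 2018 leaves years 2 to 5, which is 4.

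**The case against.** The strongest objection is that little is lost in practice.

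- **Silence is not a bar.** A reader might infer that the protocol forbids collection after removal. It does not. Section 10.4 states no consequence for data, and the provisions on adjudication, adverse events and deaths are not limited to subjects on study. Consent pages are not in the text available for review. The claim that stands is that nothing in the available text provides for collection.
- **Few subjects are likely to be affected.** Section 7.2 excludes people who are not prepared to come back for follow-up, and section 8.0 expects good retention. Most follow-up is standard care, and section 6.4 adds: "Subjects would receive continuing care from their primary physicians". A site may therefore hear of a death anyway. All of this stands and limits the exposure, but none of it is a rule for the subject who is removed.
- **The rule may no longer be able to bite.** Clinic visits end at 12 months, and on the estimated dates the last window had closed before the current version. A subject who attended through month 12 arguably keeps the annual contacts already. This largely stands, with two limits. The annual contacts sit in a section titled as the visit schedule and can be read as follow-up visits. Section 10.1 also allows the sample to be increased.
- **The 3.3 points are not specific to this rule.** They apply to any unknown vital status, and no section shows that a persistent non-attender would answer the telephone. Both remarks are correct. The figure is the cost per subject lost, not a forecast of loss.

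**Conclusion.** The point holds as a minor one. Section 10.4 allows avoidable, possibly informative loss of late vital status and event data from subjects who have not withdrawn consent, although the protocol already has a way to collect the late data without a visit. The cost is 3.3 points of best-to-worst-case range per unknown vital status at n = 30. The number of such subjects is unknown.

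Two stronger conclusions are not supported. First, a reader might infer that the main results or the safety monitoring are compromised. The primary and co-primary endpoints are fixed at exit from the catheterization laboratory (10.2.1, 10.2.2). The stopping rules in 10.3 use 30-day mortality, and 30 days is the first visit after discharge, so removal for missed visits before then is implausible. The affected outcomes are secondary or exploratory and are analysed descriptively. Second, a reader might credit the change with saving 2 to 4 contacts for every surviving subject. The gain applies only to subjects removed, or who would be removed, for non-compliance: up to 4 annual contacts each, of which 2 to 4 were still due at the 2020-08-24 version if the estimated dates hold.

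**What to change.** Restate the criterion in 10.4 so that significant non-compliance ends scheduled clinic visits only. Unless consent is withdrawn, the subject stays on study for vital status and any available clinical echo report, obtained by the telephone or local physician contact already in 6.5. For any subject still within 12 months, use the same contact to ask about death, stroke and serious adverse events. Apply this also to anyone already removed for non-compliance who has not withdrawn consent, as approvals allow.

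The cost is a short change to 10.4, a few calls, and a minor amendment. Under 14.5 the amendment needs IRB and other institutional approval before use, and submission to the regulatory authority. If the estimated dates hold, the first-year questions help nobody already treated, and the benefit lies in the remaining annual contacts for the subjects concerned.
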